5.4.7. Prior and concomitant therapy

Any medication the patient takes other than the IMP, including herbal and other non-traditional remedies, is considered a concomitant medication. At screening, patients will be asked about any previous acne treatments they have received, if applicable, as well as any concomitant medications they have taken. All prior medications taken in the 6 weeks before the first dose must be recorded in the eCRF. The last used acne treatment will be recorded independently from the period when it was used. The following information must be recorded in the eCRF for each concomitant medication: brand name, route of administration, start date, stop date, dosage, and indication. Any changes in the dosage or regimen of a concomitant medication must be recorded in the eCRF.

At each subsequent trial visit, patients will be asked whether there have been any changes to concomitant medication(s) or if any new medication(s) was/were taken since the previous site visit.

The Investigator should examine the acceptability of all concomitant procedures, medications, topical preparations and dietary supplements not explicitly prohibited in this study. In order to ensure appropriate concomitant therapy is administered, patients will be instructed to consult with the Investigator before taking any medication (either self-administered nonprescription drugs or prescription therapy prescribed by another physician).

For a detailed list of forbidden medications see Exclusion Criteria.

Medication and skin care products allowed during the trial:

- Topical mild soap-free liquid face cleansers (acid and/or pH balanced and free of abrasives and alcohol), moisturizers, sunscreens, non-comedogenic cosmetics. Patients will be asked to use the same products through all the study duration: at each subsequent trial visit, patients will be asked whether there have been any changes. Non-medicated moisturizers, soaps, and makeup should not be recorded as concomitant medications.
- Contraceptives (see Inclusion Criteria).

Prohibited medication:

- All treatment as specified in exclusion criteria.

Concomitant medications should be kept to a minimum during the clinical trial. However, if they are considered necessary for the patient's welfare and are unlikely to interfere with the study objectives, they may be allowed at the discretion of the investigator. For a detailed list of forbidden medication see exclusion criteria. In case of doubts the Sponsor should be asked.

Rescue medication:

No formal rescue medication is foreseen. Patient requiring substitutive treatment for acne, as per Investigator's judgement will be discontinued from the study and relevant details documented.

5.4.8. Treatment compliance

Patients will administer treatment at night at home, except for the first one, which will be applied at the site under the supervision of the investigator at V2/Day 1.

All missing treatment administrations documented in the diary will be counted and documented in patient's chart and in the eCRF.

In case of inadequate usage, the patient will be instructed again on the correct study medication application.

5.4.9. IMP accountability

Upon receipt of the IMP, the IWRS will be updated to acknowledge receipt. All dispensed kits (used and unused) will be collected and counted at V4 and V5. The results will be documented in the eCRF and drug account form.

5.5. Efficacy and safety variable(s)

5.5.1. Procedures

A schedule of trial procedures is provided in **Appendix A** to this trial protocol.

Screening/Baseline visits should be conducted within 14 days.

In any case, if more than 3 days occur between screening and baseline (Day1) visits, physical examination including vital signs, body weight, clinical evaluations (lesions counts, IGA, PGA) need to be repeated.

Maximal effort should be put into ensuring that study visits for school age children will be planned outside of school hours.

Screening period (Visit 1, from Day -14 to V2)

Between Day -14 and Day 1 prior to randomization patients will undergo for initial screening. Patients and parents/guardian(s) (or only one parent depending on local regulations) for minors will be allowed sufficient time to review and evaluate their participation in the clinical trial. Patients and parents/guardian(s) (or only one parent depending on local regulations) must also be notified that they are free to discontinue from the trial at any time. The patients and parents/guardian(s) (or only one parent depending on local regulations) should be given the opportunity to ask questions and allowed sufficient time to consider the written information provided. At the Screening Visit the Investigator has to ensure the Patient Compliance to the Trial.

If the patient wishes to participate, he/she will be requested to consent. After the patient and parents/guardian(s) (or only one parent depending on local regulations) has signed and dated the ICF the patient will be allocated a patient number (a combination of site and screening number), and the following screening assessments will be performed:

- Consent process documented (patient information signed and documented in source notes)
- Documentation of demographic data (age, sex, race/ethnicity, Fitzpatrick scale for skin type – see Appendix G) and food consumption habits (in terms of days per week patient consumes foods such as sweets, salty snacks, soft drinks, or other indulgent treats)
- Documentation of previous/concomitant medications/therapies
- Documentation of relevant medical, surgical and acne history (including initial diagnosis and date of first treatment of acne, if applicable)
- Physical examination* and measurements of height, body weight, vital signs (blood pressure and heart rate [pulse]) **The physical examination will focus on the skin but will also include an orientative examination of the heart, lung, abdomen, basic neurological status and general examination of the eyes, ears, nose, and throat*
- Collection of samples for determination of laboratory parameters (see Section 5.5.3):
 - Standard safety laboratory examinations
 - Blood pregnancy test in childbearing potential women (see **Appendix C** for definition of WOCBP). *If menarche occurs after the Screening visit, blood pregnancy tests will be performed at the visit where there was a change in status and according to the schedule for females of childbearing potential. For pre-menstrual patients, re-confirm pre-menses status*

at every visit and, in case of status change, collect information on contraceptive method and perform a UPT. Additional UPTs may be performed at the Investigator's discretion.

- Clinical assessments (lesion count [inflammatory and non-inflammatory lesions] and IGA/PGA)
- Check inclusion/exclusion criteria
- Recording AEs before start of treatment (= non-treatment emergent AEs, i.e. occurring after signature on consent form).

Treatment period

Visit 2 (Day 1)

- Update of concomitant medications/therapies, and AEs
- Final eligibility check of the inclusion/exclusion criteria
- The following assessments are performed also at Visit 2, and considered as baseline assessments, only if the screening visit is performed > 3 days before Visit 2, Day 1. If the screening visit is performed ≤ 3 days before Visit 2, the assessments will not be repeated during Visit 2 and will be considered as baseline assessments:
 - Physical examination and measurements of body weight, vital signs (blood pressure and heart rate [pulse])
 - Clinical assessments (lesion count [inflammatory and non-inflammatory lesions] and IGA/PGA.
- Randomization (following confirmation of in-/exclusion criteria) to one of 2 treatment arms
- [REDACTED]
- [REDACTED] (not mandatory, following specific consent)
- Assessment of local signs during the visit (before administration of first IMP dose). The patient will be questioned if he/she experienced any subjective symptoms in the past 24 hours. Presence or absence of signs/symptoms in the past 14 days will be collected, Presence or absence of overall application site irritation in the last 2 weeks will be recorded.
- Dermatology Life Quality Index (DLQI) / Children's Dermatology Life Quality Index (C-DLQI for patients from 9 to 16 years old), completed by the patient (prior to any Investigator assessments to not impact the patient's answers to the quality of life questionnaire)
- Dispensing of IMP and Patient Diary and instruction on use of IMP, administration of first dose by patient under supervision of site staff
- Schedule next visit.

Days 2–28

Daily (OD) treatment by the patient at home, in the evening after cleansing/washing, and update of diary.

T2 - Wk2, Day15 (± 2 days)

For patients aged 9 to < 12 only, a phone contact will be kept at Wk2 (in the presence of parents or legal guardian(s) (or only one parent depending on local regulations) who signed the Informed Consent), to check concomitant medications/therapies, IMP compliance, AEs and assessment of local tolerability by local signs/symptoms (the patient will be questioned if he/she experienced any of these subjective symptoms from the last visit, by checking the diary).

Patients will also be asked to report signs and symptoms experienced within the last 24 hours prior to the phone contact.

The Investigator must promptly record the call results in the eCRF. In case of safety issues, an immediate automatic notification will be sent to the DSMB.

Visit 3 (Wk4, Day 29) (± 2 days)

- Check concomitant medications/therapies and AEs
- Physical examination and measurements of vital signs (blood pressure and heart rate [pulse])
- Clinical assessments (lesion count [inflammatory and non-inflammatory lesions] and IGA/PGA). PGA will be evaluated only if the trunk is treated
- Assessment of local tolerability by local signs/symptoms. The patient will be questioned if he/she experienced any of these subjective symptoms within the last 24 hours prior to the visit
- Collection of diary and assessment of patient compliance by diary check
- Dispensing a new diary
- Schedule next visit.

Days 29–56

Daily treatment (OD) by the patient at home, in the evening after cleansing/washing, and update of the diary (including the day of the V3/Wk4).

Visit 4 (Wk8 Day 57) (± 2 days)

- Check concomitant medications/therapies and AEs
- Physical examination and measurements of vital signs (blood pressure and heart rate [pulse])
- Clinical assessments (lesion count [inflammatory and non-inflammatory lesions] and IGA/PGA). PGA will be evaluated only if the trunk is treated

- Assessment of local tolerability by signs/symptoms. The patient will be questioned if he/she experienced any of these subjective symptoms within the last 24 hours prior to visit
- Collection of IMP and diary and assessment of patient compliance by diary check, and counting of tubes
- Dispensing of IMP and diary
- Schedule next visit.

Days 57–84

Daily treatment (OD) by the patient at home, in the evening after cleansing/washing, and update of the diary (including the day of the V4/Wk8). Treatment should be discontinued the night before EoT.

T10 - Wk10, Day71 (\pm 2 days)

For patients aged 9 to < 12 only, a phone contact will be kept at Wk10 (in the presence of parents or legal guardian(s) (or only one parent depending on local regulations) who signed the Informed Consent), to check concomitant medications/therapies, IMP compliance, AEs and assessment of local tolerability by local signs/symptoms (the patient will be questioned if he/she experienced any of these subjective symptoms from the last visit, by checking the diary).

Patients will also be asked to report signs and symptoms experienced within the last 24 hours prior to the phone contact.

The Investigator must promptly record the call results in the eCRF. In case of safety issues, an immediate automatic notification will be sent to the DSMB.

Visit 5 (Wk12, end of treatment [EoT] Day 85 (+ 3days)

- Check concomitant medications/therapies and AEs
- Physical examination, body weight and height (for minors) and vital signs (blood pressure and heart rate [pulse])
- Collection of samples for determination of laboratory parameters:
 - Standard safety laboratory examinations
 - Blood pregnancy test in childbearing potential women (see **Appendix C** for definition of WOCBP)
- Clinical assessments (lesion count [inflammatory and non-inflammatory lesions] and IGA/PGA). PGA will be evaluated only if the trunk is treated
- Assessment of local tolerability by local signs/symptoms. The patient will be questioned if he/she experienced any of these subjective symptoms within the last 24 hours prior to visit
- Patient's assessment of overall application site irritation

- [REDACTED]
- [REDACTED] (not mandatory, following specific consent)
- Dermatology Life Quality Index (DLQI) / Children's Dermatology Life Quality Index (C-DLQI for patients from 9 to 16 years old), completed by the patient (prior to any Investigator assessments to not impact the patient's answers to the quality of life questionnaire)
- Collection of IMP and diary and assessment of patient compliance by diary check, and counting of tubes
- Schedule next visit.

Follow-up

Visit 6 (Wk14) End of trial Day99 (+ 2days) or ETV in case of withdrawal after EoT – Telephone contact

- Check concomitant medications/therapies and AEs
- End of trial.

If clinically significant out of range or clinically significant values are found at V5, patient will be asked to return at site to perform additional laboratory examinations of the significant out of range values.

This visit will be performed only for patients who are not included in the long-term study.

UNSCHEDULED VISITS (Early termination visit [ETV])

Any time the trial is permanently discontinued for any reason during the treatment phase, an Early Termination visit should be performed:

- Check concomitant medications/therapies and AEs
- Physical examination and measurements of vital signs (blood pressure and heart rate [pulse])
- Collection of samples for determination of laboratory parameters:
 - Standard safety laboratory examinations
 - Blood pregnancy test in childbearing potential women (see **Appendix C** for definition of WOCBP)
- Clinical assessments (lesion count [inflammatory and non-inflammatory lesions] and IGA/PGA). PGA will be evaluated only if the trunk is treated
- [REDACTED]
- [REDACTED] (not mandatory, following specific consent)

- Dermatology Life Quality Index (DLQI) / Children's Dermatology Life Quality Index (C-DLQI for patients from 9 to 16 years old), completed by the patient (prior to any Investigator assessments to not impact the patient's answers to the quality of life questionnaire)
- Evaluation of local tolerability signs/symptoms. The patient will be questioned if he/she experienced any of these subjective symptoms within the last 24 hours prior to visit
- Patient's assessment of overall application site irritation
- Collection of IMP and diary and assessment of patient compliance by diary check, and counting of tubes
- End of trial.

In case the discontinuation is during the Follow-up phase, the Visit 6 (Wk14) End of trial (± 2 days) – Telephone contact procedures will be performed.

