5.1. Overall trial design and plan - description

This is a multicenter, randomized, parallel-group, vehicle-controlled, double-blind, efficacy and safety study. At least 40 sites located in at least 5 European countries will participate in this trial.

[figure not shown]
Approximately 400 patients (males and female aged ≥ 9 and <50 years) affected by facial acne vulgaris are planned to be randomized in order to have at least 366 patients in the full analysis set (FAS) and will be randomly allocated to one of the 2 treatment arms (NAC-GED-0507-34-Levo ■% gel, or vehicle gel) in a 1:1 ratio. Recruitment will be competitive between the sites.

Stratified randomization will be conducted to guarantee the followings:

- Subset 9 to < 12 years: 5% of patients, corresponding to 20 patients.

The trial design consists of a 14-day screening period, a 12-week comparative treatment period, and a 2-week treatment-free follow-up period. Each patient will have 6 visits: V1-screening, V2-Day 1, V3/Wk4-Day 29, V4/Wk8-Day 57, V5/Wk12-Day 85 (EoT) (primary endpoint visit), V6/Wk14-Day 99 safety follow-up visit (Phone contact). Patients who complete 12 weeks of treatment can be eligible to continue treatment with NAC-GED-0507-34-Levo gel ■%, in a separate open-label long-term study NAC-GED-0507-ACN-01-23-LT (GEDACNE-LT). In this case, the V6/Wk14-Day 99 follow-up visit (Phone contact) will not be performed. (**Figure 1**). Additionally, two telephone contacts will be performed in 9 to < 12 years old patients, at Wk2 and Wk10.

Figure 1- Study design

IMP will be topically applied OD by the patient to the entire face (including nose; avoiding eyelid and lip region) and to skin areas of the trunk accessible for self-application (shoulders, upper back, and upper anterior chest) if those are affected by acne. The study medication is applied by patients at home, except for the first dose, which will be applied at the site (V2, Day 1) under the Investigator's or study nurse's supervision. The gel will be applied to dry and, cleansed skin at night, following the instructions received at the site by the Investigator/study nurse on the correct method of IMP application.

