8.3. Discontinuation of trial treatment or trial participation for individual patients

8.3.1 Premature discontinuation of trial treatment

The trial patient can have his/her trial treatment terminated prematurely at any time, without having to give reasons.

Patients will be withdrawn from the treatment if their safety or well-being is at risk. Discontinuation will be made at the discretion of the investigator/Sponsor/DSMB or at the patient's request.

The investigator should contact the Sponsor to discuss the withdrawal of a patient who fulfils the discontinuation criteria, prior to discontinuing a patient from the study, unless in those circumstances where the investigator considers that the patient is at immediate clinical risk.

A patient must be discontinued under the following circumstances:

- Withdrawal of consent
- IMP permanent discontinuation for any reason in one or both treated areas
- Pregnancy
- An AE, including intercurrent illness for which the patient desires to discontinue treatment or the investigator determines that it is in the best interest of the patient to be discontinued
- In case of unexpected laboratory out-of-range values in the blood samples collected at screening, which in the Investigator's opinion may pose the patient at increased risk during participation to the clinical trial the patient will be contacted to discontinue the treatment and will be withdrawn from the study.
- Serious concomitant symptoms (e.g., extensive blisters or erosions) in the facial area as well as a local or generalized allergic reaction to the IMP or procedures
- Lost to follow-up.

A patient may be required to discontinue from the trial at any time for the following reasons:

- The patient's treated and not treated acne worsens and requires alternative or supplemental medication during the trial.
- Occurrence of another dermatosis requiring treatment that interferes with the inclusion criteria
- Subsequent disclosure that the inclusion and exclusion criteria were not fulfilled when the patient was enrolled in the trial if the safety and well-being of the patient might be influenced
- At the discretion of the investigator
- Non-compliant use of IMP or protocol requirements
- Treatment code is broken.

In the case trial treatment of a patient has been stopped prematurely, ETV procedures should be conducted as far as possible. The DSMB will be informed accordingly, and all the relevant information provided.

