40. [name] CC, Jourdan E, Picardo M. Acne is an inflammatory disease and alterations of sebum composition initiate acne lesions. *J Eur Acad Dermatol Venereol.* 2014;28:527-32

12. Appendix A

[figure not shown]
ACTIVITIES ¹⁵	Screening ¹	Baseline/ First Dose	Phone Contact (for 9 to < 12 years old) ⁹	Treatment and Evaluations		Phone Contact (for 9 to < 12 years old) ⁹	End of Treatment (EoT) ¹²	Follow-up or ETV after EoT (Phone contact) ¹³	ETV (Withdrawal)
	Visit – Week	V1	V2	T2/Wk2	V3/Wk4	V4/Wk8	T10/Wk10	V5/Wk12	V6/Wk14
	Day -14/1	Day 1	Day 15 (±2)	Day 29 (±2)	Day 57 (±2)	Day 71 (±2)	Day 85 (+3)	Day99(+2)	ANY TIMES
Informed consent / Informed assent signature (if applicable)	X								
Demography	X								
Medical history	X								
Physical examination	X	X ⁵		X	X		X		X
Prior medications	X								
Vital signs	X	X ⁵		X	X		X		X
Body weight and height	X	X ⁵					X ¹⁸		
Blood pregnancy test, if applicable ²	X						X		X
Laboratory tests ³	X						X	X ³	X
Lesion count, separately for inflammatory and non- inflammatory lesions	X	X ⁵		X	X		X		X
Investigator’s Global Assessment (IGA) -FACE	X	X ⁵		X	X		X		X
Physician Global Assessment (PGA) – TRUNK ¹⁴	X	X ⁵		X ¹⁴	X ¹⁴		X ¹⁴		X ¹⁴
Eligibility evaluation	X	X ⁵							
Assessment of local tolerability- Application site signs/symptoms		X ¹⁶	X	X	X	X	X		X
Assessment of overall application site irritation		X ¹⁷					X		X
Enrollment and randomization		X							
Study medication supply delivery ⁴		X			X				
Study medication application at site ⁶		X							
Study medication supply return and accountability					X		X		X
Diary dispensing		X		X	X				
Diary return				X	X		X		X
Adverse events monitoring ⁷	X	X	X	X	X	X	X	X	X
Concomitant medication intake monitoring	X	X	X	X	X	X	X	X	X
Patient’s compliance assessment by diary check (or questions during phone contact)			X	X	X	X	X		X
DLQI or C-DLQI ⁸		X					X		X
██████████		X					X		X
██████████		X					X		X

1. Screening procedure should be completed within 14 days

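### Patients who stop during treatment leave the trial at the early termination visit with no scheduled later question about new adverse events; the existing Visit 6 call could cover them cheaply

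*Protocol*

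**What the plan says.** **Stopping the gel ends participation.** Protocol section 8.3.1 lists, among the reasons for which a patient must be discontinued, "IMP permanent discontinuation for any reason in one or both treated areas".

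**What follows a stop during treatment.** Section 5.5.1: "Any time the trial is permanently discontinued for any reason during the treatment phase, an Early Termination visit should be performed". That visit covers AEs, concomitant medication, physical examination, vital signs, laboratory tests, acne assessments, local tolerability and overall irritation. Its last item closes the trial for the patient.

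**Who gets the V6 call.** The sentence after that list begins "In case the discontinuation is during the Follow-up phase, the Visit 6 (Wk14) End of trial" and gives the telephone procedures to those patients. Of V6 itself, section 5.5.1 says: "This visit will be performed only for patients who are not included in the long-term study". The schedule table in Appendix A heads the V6 column "Follow-up or ETV after EoT (Phone contact" and keeps a separate column for the withdrawal ETV.

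**The design description.** Section 5.1 speaks of "a 2-week treatment-free follow-up period. Each patient will have 6 visits". It names one exception, roll-over into the long-term study: "In this case, the V6/Wk14-Day 99 follow-up visit (Phone contact) will not be performed".

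**Other safety provisions.** Section 7.1 has AEs still present after the last scheduled visit followed within 14 days of the last dose, by call or visit, and monitored until they subside. It also requires AEs after the end of the trial to be reported if the investigator thinks them related. Section 10.3 has patients told to contact the investigator about any health problem. Sections 8.3.1 and 8.3.2 have the DSMB informed of premature stops. Section 8.5 sets the end of the trial at the last patient's last visit.

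**The concern.** The incidence of treatment-emergent AEs is a stated safety endpoint (section 6.4), and the synopsis describes V6 as a call made for safety monitoring. A patient who finishes 12 weeks and does not roll over is asked about AEs once more after a treatment-free interval. A patient who stops in week 3 or week 7 is asked at the ETV and, by schedule, not again. Such a patient cannot be picked up by the long-term study either, since sections 5.1 and 8.4 offer it only to patients who complete treatment.

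At stake is slightly incomplete capture of new AEs that begin after the ETV and that nobody volunteers. The visit schedule is protocol content, so a statistical analysis plan could not supply the contact.

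**Working it through.** The plan states no figure on this point, so there is nothing of its own to reproduce. The check has three parts.

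**1. Exit routes side by side (sections 5.1, 5.5.1, 8.3.1, 8.4; Appendix A)**

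- Completes treatment, does not roll over: V6 call.
- Withdraws after end of treatment: V6 procedures.
- Completes treatment and rolls over: no V6 in this trial, but continues in the long-term study.
- Stops during treatment: ETV, then end of trial. No later trial contact is scheduled. Sections 8.3.2 and 8.4 refer to follow-up outside the trial and standard of care.

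The section 7.1 contact is triggered by an AE still present at the last scheduled visit. It is not a general question about new AEs.

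**2. Time from last dose to V6 for completers**

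- Visit 5 is Day 85 (+3), so Day 85 to 88. The last dose is the day before, so Day 84 to 87.
- V6 is Day 99 (+2), so Day 99 to 101.
- Shortest interval: 99 − 87 = 12 days. Longest: 101 − 84 = 17 days.

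For the ETV, Appendix A sets no offset from the last dose, so a late ETV may already cover part of this period.

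**3. Size**

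*Number of early terminators.* The protocol shows no early-termination rate. The difference 400 − 366 = 34 (34/400 = 8.5%) is an allowance for non-evaluable patients, which is a different quantity. I assume 5% to 15%:

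- 0.05 × 400 = 20
- 0.15 × 400 = 60

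*Chance of a new AE in 14 days.* Section 3.2 reports that 16% to 19% of patients per arm had one or more AEs in the earlier controlled study. I assume a constant hazard over T = 84 days (12 weeks) or T = 98 days (14 weeks):

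h = −ln(1 − p)/T; chance in 14 days = 1 − exp(−14h)

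| p | T = 98 | T = 84 |
|---|---|---|
| 0.16 | 0.0246 | 0.0286 |
| 0.19 | 0.0297 | 0.0345 |

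*Patients with a new AE in the 14 days:*

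- Low: 20 × 0.0246 = 0.49
- High: 60 × 0.0345 = 2.07

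This range of about 0.5 to 2.1 patients leans high as a measure of what is missed. It counts AEs of any cause. It does not subtract patients who withdrew consent or were lost, patients already contacted under section 7.1, events volunteered as instructed, or ETVs held some days after the last dose.

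**The case against.** The strongest reply is that the patients one would worry about most are already followed. Section 8.3.1 makes serious local symptoms a reason to stop, "as well as a local or generalized allergic reaction to the IMP or procedures". If such an event is unresolved at the ETV, section 7.1 keeps the patient in contact within 14 days of the last dose and until symptoms subside. The DSMB is told of the stop, and the ETV itself is a full safety examination. This stands. It limits the gap mainly to patients with no ongoing AE at the ETV, for whom a later call is likely to yield least. A reader might infer that there is no AE follow-up at all after the ETV, or that patients who stop because of a reaction are left unobserved. Section 7.1 rules out both readings.

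A second reply is that section 5.1 is not contradicted. Its count of visits describes the planned course, which a patient who stops early will not complete. V6 is not universal in any case, since roll-over patients skip it. This also stands: a reader might infer a breach of an internal standard, but the protocol sets no such standard.

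A third reply is that the restriction of V6 to patients outside the long-term study could be read to include early terminators. This does not hold up. The ETV list closes the trial, and the next sentence gives the V6 procedures to discontinuations in the follow-up phase. If the wider reading was intended, the text still needs correcting, and Day 99 would not be tied to the patient's own last dose.

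Finally, the time uncovered is unknown, because the ETV has no fixed offset from the last dose. This is accepted and is built into the fix.

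**Conclusion.** The point holds in a narrow form. Patients who stop during treatment have no scheduled question about new AEs after the ETV, whereas completers who do not roll over are asked 12 to 17 days after the last dose. The gap is confined to new AEs that are not volunteered, mainly in patients with nothing ongoing at the ETV.

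Its size is at most about 0.5 to 2.1 patients. That rests on an assumed 5% to 15% early-termination rate and on the earlier study's AE percentages applied at an assumed constant rate. Patients who stopped early may not share that rate, so the figure is an order of magnitude only.

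A reader might go on to infer bias between arms or an effect on the efficacy result. The documents support neither: the rule is the same in both arms and touches no efficacy assessment. A volunteered AE remains recordable until the trial ends under section 8.5; after that, AEs judged related must still be reported. This is a minor point, worth making because the remedy costs so little.

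**What to change.** In section 5.5.1 and Appendix A, extend the V6 telephone contact (AEs and concomitant medication) to every patient with a treatment-phase ETV who can be reached and agrees. Time it about 14 days after that patient's last dose instead of at Day 99. Waive it when the ETV itself falls 14 or more days after the last dose, and combine it with any follow-up contact already due under section 7.1.

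The cost is amendment wording and one call per early terminator: at most 20 to 60 calls under the assumed 5% to 15% rate, and fewer where the call is waived or combined. No site visit, new procedure or change to the efficacy analysis is needed.
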